2.3 POTENTIAL RISKS AND BENEFITS

2.3.1 Known Potential Risks

There are minimal anticipated risks or harms to the participant. One possible risk is breach of confidentiality should a data breach occur. Regarding the risk of breach of confidentiality, we, the study sponsor (Pivot Health Technologies Inc., formerly Carrot Inc.) comply with HIPAA and state this risk in our privacy and terms of use on our website regarding use of Pivot. As such, we adhere to HIPAA's Breach Notification Rule should a data breach occur. We take careful measures to prevent a data breach including use of encryptions, secure connections, and limited access to data (see section 10.1 "Data Collection and Confidentiality"). The sponsor uses appropriate safeguards and complies, where applicable, with 45 C.F.R. Part 164, Subpart C with respect to Electronic Protected Health Information, to prevent use or disclosure of Protected Health Information. Specifically, Pivot Health Technologies Inc. has implemented the administrative, physical, and technical safeguards set forth in 45 C.F.R. §§ 164.308, 164.310, and 164.312 that reasonably and appropriately protect the confidentiality, integrity, and availability of any Protected Health Information that it creates, receives, maintains, or transmits. The QuitGuide app is maintained by the U.S. Government. It is protected by various provisions of Title 18, U.S. Code. The QuitGuide app notes, "NCI complies with requirements for privacy and security established by the Office of Management and Budget (OMB), Department of Health and Human Services (DHHS), and the National Institutes of Health (NIH)."

Another possible risk is participant anxiety, which could be related to using the Pivot Breath Sensor during the study, or completing biovalidation using the Pivot Breath Sensor on study videocalls. For regular use of the Pivot Breath Sensor during the study, while there are suggested breath sampling patterns provided with the breath sensor packaging, participants will ultimately sample at their discretion. No medical

decisions are made based on study data. For completing biovalidation, participants will be fully informed why the biovalidation is being performed, what it tests for, and they will be asked on each applicable videocall if they feel comfortable proceeding with biovalidation. Participant compensation is not based on breath sampling frequency or results, or on biovalidation results.

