2.3.3 Risk Benefit Assessment

Given the non-invasive nature of Pivot and QuitGuide and study data collection, there are minimal anticipated risks. These risks relate to breach of confidentiality in the circumstance of a data breach, possible participant anxiety related to using the Pivot Breath Sensor or related to performing biovalidation with the sensor during videocalls, and possible side effects of the use of over-the-counter NRT if the participant chooses to use it. These risks have been mitigated to the extent possible through data protection measures, through enabling participants to ultimately decide if and when to do breath samples, through fully informing participants why the biovalidation is being done, what it tests for and asking if they would like to proceed with the testing on the applicable videocalls, and through enabling participants to make an informed decision on if they will use NRT and which NRT they will use if they choose to use any at all. Breath samples, biovalidation, NRT selection and NRT use are at the participant's discretion and are not mandated. Indeed, no specific use of Pivot or QuitGuide overall is required. Participants will have the remote support of study staff and customer support as they need over the course of the study. Participants are not required to change their smoking behavior. No medical decisions are made based on study data.

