- Number of quit attempts at 4, 12, 26, 52, and 104 weeks (defined as answering ≥ 1 to the following question: “Since you began the study, how many times have you tried to quit smoking where you've gone at least 1 day without smoking a cigarette, even a single puff?”).
- User satisfaction with the smoking cessation program (set-up and getting started with program, recommend to friend, program design, program was useful for quitting, program helped me quit, program helped me stay quit) at 2, 3, 4, 5, 12, 26, 52 and 104 weeks
- Engagement with program, collected weekly during the first 12 weeks after enrollment:
 - Number of times app opened (self-report)
 - Number of days in which app was opened (self-report)
 - Number of weeks in which app was opened (self-report)
- Participant changes in self-efficacy at 6, 12, 26 and 52 weeks
- Participant changes in self-reported health and wellbeing at 26 and 104 weeks
- Self-reported NRT use at 4, 8, 12, 26, 52 and 104 weeks
- Use of other smoking cessation tools (apps, counseling, non-study medications, etc.) at 12, 26, 52, and 104 weeks
- Alcohol use behavior at 12, 26 and 52 weeks (Alcohol Use Disorders Identification Test-Concise or AUDIT-C screening questionnaire, 3 items) [18-20]
- Presence of depressive symptoms screening at 12, 26, and 52 weeks (Center for Epidemiological Studies Depression Scale or CES-D screening questionnaire, 10 items) [11,21-23]
- Living and social environment relating to cigarette smoking at 12, 26 and 52 weeks (live with other adults who smoke, live with romantic partner who smokes, number of close friends who smoke)
- Adverse events at 26, 52 weeks

Eligibility Criteria

The study population comprises current smokers, 21 years of age and above, who own and

regularly use a smartphone and are ready to quit smoking in the next 30 days.

Inclusion Criteria

- 21+ years of age
- Current daily cigarette smokers (at least 5 cigarettes per day) for the past 12 months
- Plans to quit smoking in the next 30 days
- Resident of the United States
- Able to read and comprehend English
- Owns and uses a smartphone compatible with the study app (iPhone 5 and above with operating system iOS 12 and above, or, Android 7.0 and above with operating system Android 7.0 and above)
- Has daily internet access on smartphone
- Comfortable downloading and using smartphone apps
- Willing to sign the Informed Consent Form

Exclusion Criteria

- Pregnancy (self-reported)

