7.9 USER MANUAL AND TRAINING

Both Pivot and QuitGuide were designed with the intention that users are able to understand how to use these programs independently. For the Pivot Breath Sensor, a Quick Start Guide, Package Insert, Educational Booklet and package labeling are included with the device to aid the user and an online User Manual [REDACTED] is also available. All of these items will be accessible to study participants in the intervention arm; in addition, a phone number will be included within the labeling material to contact customer support. QuitGuide provides technical support to help users download and use the app through [contact].

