8.5 BIOVALIDATION

Biovalidation will be sought at 12, 26, 52 and 104 weeks in individuals who reported 7-day (or greater) PPA on the associated questionnaire (from 12, 26, 52 or 104 weeks). A videocall will be scheduled for within 7 days following the participant's response to the associated questionnaire. At the beginning of each biovalidation call, participants will be asked 7-day PPA status. Participants will be asked (yes/no) if they have smoked any other non-cigarette (ex. pipes, cigars, hookah) or combustible materials (ex. cloves, marijuana) over the last 24 hours. They will also be asked how many cigarettes they currently smoke per day. Participants who indicate they are not at least 7 days abstinent (i.e., answer "Yes" to the following question: "In the last 7 days have you smoked any cigarettes, even a single puff?") and/or indicate they currently smoke cigarettes will not be eligible to undergo further biovalidation testing during the visit. Participants who indicate they are at least 7 days abstinent and do not smoke cigarettes will be eligible to proceed with the testing. Participants who indicate they have smoked any other combustible materials over the previous 24 hours will be eligible to undergo biovalidation test, with the option to schedule a follow-up biovalidation test for the following day with instruction to not smoke the previously reported other combustible substance(s) over the intervening 24-hour period. If a participant is eligible for biovalidation and biovalidation is not achieved, the reason will be noted (ex. did not complete a biovalidation study visit, reported relapse so biovalidation visit was not completed, participant's breath CO sample was 10 ppm or more, etc.).

If this is the first study biovalidation visit a participant has participated in, the steps of the visit and the CO breath sample will be described in detail, with questions fielded and verbal confirmation the participant would like to proceed obtained before doing the biovalidation test. If this is not the first study biovalidation visit a participant has participated in, there will be a high-level review of the steps of the visit and the CO

breath sample, with questions fielded and verbal confirmation that the participant would like to proceed obtained.

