Biovalidation will be obtained through CO breath sampling. For the 12-, 26- and 52-week biovalidation visits, participants in the intervention arm will use their Pivot Breath Sensor for this test. Participants in the control arm will be mailed a Pivot Breath Sensor prior to the visit that has a limited number (10 or less) of samples it can perform. For the 104-week biovalidation visit, all eligible participants who schedule the biovalidation visit will be mailed a Pivot Breath Sensor. On the call, participants will have the process of giving a breath sample described to them. They will be offered the chance to ask questions, and then study staff will provide an overview of the steps to give a breath sample. When they feel ready, they will give a breath sample and hold the breath sensor up to the screen immediately after completing the sample so that study staff on the videocall can see the CO ppm measurement on the breath sensor screen. A CO ppm value of less than 10 will be considered consistent with abstinence.[16]

After their first biovalidation visit, participants in the control arm will be instructed to not use the breath sensor beyond the visit, and to place the sensor in a safe place (for example, in the original packaging, in a closet) for use at a future biovalidation visit, should there be one. For future biovalidation visits, participants will use their existing breath sensor or will be sent a new one (fully functioning breath sensors for the intervention arm and sensors limited to 10 breath samples for the control arm for 12-, 26- and 52-week visits; and fully functioning sensors for all eligible participants for the 104-week visit) as needed. Participants will keep the breath sensor. While the sponsor will not request the sensors be mailed back, participants may mail their sensor(s) back to the sponsor if they prefer.

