10.2 ADVERSE EVENTS

Participants will be asked to detail any issues with their assigned smoking cessation program and/or NRT on the 26- and 52-week questionnaires. In addition, participants may offer up such issues at any point during the study by reaching out to study staff and/or customer service. The study sponsor follows a department operating procedure (DOP-1748, Clinical Adverse Event Reporting, [REDACTED]) for adverse event

reporting. In accordance with the sponsor's adverse event policy, Quality Assurance will be made aware of these issues. Additional information will be sought from participants reporting issues, as needed. Upon collection of adequate information on the issue, or an adequate good-faith effort to obtain such information, a determination will be made regarding any associated reporting requirements, in compliance with DOP-1748 and Quality Assurance reporting policies.

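### The adverse-event question covers breath-sensor problems in Pivot but not in control, names the biovalidation call in neither arm, and is last asked before the week-52 and week-104 calls

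*Combined protocol and SAP*

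**What the plan says.** Section 10.2 describes the solicited part of adverse-event collection in one sentence: participants are asked about problems with their assigned "program and/or NRT on the 26- and 52-week questionnaires". Section 7.3 lists the matching secondary outcome as "Adverse events at 26, 52 weeks". Section 10.2 adds that participants may raise such issues with study staff or customer service at any time.

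The risk sections look wider than that. Section 2.3.1 ties possible anxiety to use of the sensor and to "completing biovalidation using the Pivot Breath Sensor on study videocalls". Section 2.3.3 repeats it among the three kinds of risk it lists: "possible participant anxiety related to using the Pivot Breath Sensor or related to performing biovalidation with the sensor during videocalls". Neither section confines the biovalidation part to one arm.

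Section 6.1 makes the sensor a component of Pivot. The Synopsis and section 5 define the control as QuitGuide with optional NRT. Control participants meet the sensor only through biovalidation; section 8.5 says of the week-12, 26 and 52 visits: "Participants in the control arm will be mailed a Pivot Breath Sensor prior to the visit". At week 104, every eligible participant who schedules the visit is mailed one.

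On order, section 8.5 says the "videocall will be scheduled for within 7 days following" the participant's questionnaire response. Under section 8.7, for a participant who does the week-104 visit, its completion (or week 110, if sooner) ends the study.

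**The concern.** A risk that the protocol names should be covered by the way adverse events are collected, and equally in both arms where both are exposed. Here the question is framed around the assigned program and NRT, and a biovalidation call is a measurement procedure that belongs to neither. Two consequences follow from the text. A sensor problem during a call is solicited in one arm and not in the other, so a by-arm listing of this secondary outcome would rest on unequal ascertainment for a shared exposure. And because the question comes before the call at each time point, the later calls have no solicited question after them. What is at stake is the completeness and between-arm comparability of the adverse-event outcome. The primary endpoint (app opens at 12 weeks) and the sample size are not involved.

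**Working it through.** The plan gives no figure to reproduce. The check sets scope against exposure, then counts along the timeline.

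**Inputs**
- Solicited question: weeks 26 and 52; assigned program and/or NRT (7.3, 10.2).
- Biovalidation calls: weeks 12, 26, 52 and 104, for those reporting 7-day abstinence (8.3, 8.4, 8.5).
- Order: each call follows the response to the questionnaire of the same time point (8.5).
- Program content: Pivot includes the sensor (6, 6.1); control is QuitGuide plus optional NRT (Synopsis, 5).

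**Step 1: scope.** For a Pivot participant, a sensor problem is a problem with the assigned program, so it is in scope. For a control participant, the sensor is part of neither QuitGuide nor NRT, so the same problem is out of scope. The videocall is not named for either arm.

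**Step 2: timing.** For each call, find the next questionnaire that carries the question.

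| Call (week) | Next solicited question | Nominal gap | Sensor problem solicited, Pivot | Sensor problem solicited, control |
|---|---|---|---|---|
| 12 | week 26 | 26 − 12 = 14 weeks | yes | no |
| 26 | week 52 | 52 − 26 = 26 weeks | yes | no |
| 52 | none (the week-52 item precedes the call) | – | no | no |
| 104 | none | – | no | no |

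Calls with no later solicited question, either arm: 4 − 2 = 2 of 4. Calls after which a sensor problem is within the solicited scope: 2 of 4 in Pivot, 0 of 4 in control. Where a later question exists, the nominal gap is 14 or 26 weeks, shortened by the few days between questionnaire and call.

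**Step 3: other channels.**
- *Spontaneous reporting (10.2).* Open throughout, in both arms. The sentence refers back to program and NRT issues, and it is not solicitation.
- *Comfort check (2.3.1, 8.5).* Asked on each applicable call in both arms, before the sample. It cannot record distress during or after the test.
- *Reason noted (8.5).* Applies when an eligible participant's biovalidation is not achieved. It misses distress in someone who completes the test with a qualifying value.
- *CES-D (7.3).* Screens for depressive symptoms at weeks 12, 26 and 52. It is not described as adverse-event collection, and it too comes before the week-52 call.

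None of these is described as feeding solicited adverse-event data about a completed test.

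**The case against.** The best reply is that the finding rests on a summary sentence. The schedule of activities is redacted, the adverse-event operating procedure is cited but not shown, and the literal questionnaire and call script are not visible. The revision history also shows that the call holds more than section 8.5 describes: Rev 5 added questions on possible carbon monoxide exposure sources, which 8.5 does not mention. A closing question on distress might already be in the script. This stands as a limit on certainty. It does not change what 10.2 and 7.3 commit the trial to collect.

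Four stronger readings are tempting, and the documents do not support them.
- *Control participants have nowhere to report a sensor or call problem.* They may contact study staff or customer service at any time (2.3.3, 10.2), and trained staff are live on every call.
- *The named risk cannot be checked against trial data at all.* A refusal caused by anxiety would be noted under 8.5, and section 11.1 makes the calls a data source. What is missing is systematic capture after a completed test.
- *Control participants are denied the sensor's labeling.* Section 7.9 says of the labeling, "All of these items will be accessible to study participants in the intervention arm", but does not say that controls lack it. Section 6.2 lists the guides as contents of the sensor package, and 8.5 suggests controls store the sensor in its original packaging. Section 7.8 can be read as listing program components only.
- *The number of people eligible for biovalidation measures the harm.* Applying abstinence rates from the earlier Pivot cohort would give the number who might take a test, not the number with a problem. The documents give no event rate.

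It is also fair that exposure differs by arm. Regular sensor use belongs to Pivot, while control sensors for the first three visits allow at most 10 samples. Some difference in sensor reports would therefore be real. Section 11.2 specifies no between-arm test of adverse events that unequal ascertainment could distort. The shared exposure on the call remains.

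**Conclusion.** The point holds as a low-severity gap. Read as written, solicited adverse-event collection covers sensor problems in Pivot and not in control, names the biovalidation call in neither arm, and leaves 2 of 4 calls (weeks 52 and 104) without a later question in both arms. The existing safeguards apply to both arms and soften the gap without closing it. The conclusion assumes that the questionnaire follows the scope given in 10.2 and that calls follow the order in 8.5. If the unseen script already asks about distress after the sample, the remaining task is to say so in the protocol. The protocol rates the risk as minimal, the test is voluntary, and only people reporting abstinence are invited, so few or minor events are a reasonable expectation. No size of harm can be given from the documents.

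**What to change.** Add one fixed closing question to every biovalidation call, in both arms and at weeks 12, 26, 52 and 104: any problem or distress with the breath sample, the sensor or this call. Record the answer and route it through the section 10.2 process, and list these time points beside the adverse-event outcome in section 7.3. Extend the week-26 and week-52 questionnaire item to name the breath sensor and biovalidation calls alongside the assigned program and NRT, with the same wording in both arms.

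The calls are already staffed and already collect data, so no visit or staff is added. The cost is a protocol and script wording change, plus a few more minor reports to process.

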10.3 DATA SAFETY MANAGEMENT BOARD

As the study interventions of app-based smoking cessation programs and over-the-counter NRT are standard and low-risk, a data safety monitoring board is not used. This is aligned with a recent RCT with similar design, which assessed web- and social-media based quit programs combined with NRT.[29]

11. STUDY RESULTS

11.1 DATA COLLECTION AND CONFIDENTIALITY

The study sponsor follows a department operating procedure (DOP-1749, [REDACTED]) for clinical data management. Participants will be assigned a unique participant ID which will be used for data collection. Data collection will take place on electronic case report forms (CRFs) via online questionnaires completed by study participants, through data collected in the Pivot app and on the biovalidation videocalls. The biovalidation videocalls will be conducted on a HIPAA-compliant version of a video call platform (Zoom or Google Meet). CRFs will be reviewed by the study team prior to the end of the study to ensure completeness. Based on this review, additional or complete data will be sought from participants as needed. Access to electronic CRFs will be limited to necessary study personnel. Study data will be kept in a secure database by the investigator. This database will be accessible only by necessary study personnel. The database will not contain personal identifying information; all subject data in the database will be associated with study identification numbers. The data will be kept for a minimum of 5 years. The data shall be retained for a maximum period of time that is equivalent to the design and expected life of the Pivot smoking cessation product or the duration of the study sponsor's (Pivot Health Technologies Inc., formerly Carrot Inc.) existence, whichever is the shortest of the two.

Regarding use of Pivot, associated data will be accessed by study investigators with the Pivot app, including data on the use of the Pivot Breath Sensor. This app is the commercially available Pivot app. With regard to the information we will collect, we, the study sponsor, associate each logged-in user to a user ID that is a unique identifier which is generated randomly on account creation. We will periodically synchronize logs from the sensor and upload them based on this user ID only. The breath samples we collect only contain information regarding: sample ID, type, value, and time. When we upload this breath sample information, the only additional information included would be the Pivot app build information and user's breath sensor ID. Through the Pivot app, we are able to assess user app engagement characteristics such as time and duration of app openings and content accessed. We are also able to assess user inputs into the app such as cigarette logging, responses to questions asked during activities, quit dates, and the ordering of NRT. We comply with HIPAA and state this in our privacy and terms of use on our

website. As such we adhere to HIPAA's Breach Notification Rule should a data breach occur. We take careful measures to prevent a data breach including use of encryptions, secure connections, and limited access to data. We use appropriate safeguards and comply, where applicable, with 45 C.F.R. Part 164, Subpart C with respect to Electronic Protected Health Information, to prevent use or disclosure of Protected Health Information. Specifically, Pivot Health Technologies Inc. (formerly Carrot Inc.) has implemented the administrative, physical, and technical safeguards set forth in 45 C.F.R. §§ 164.308, 164.310, and 164.312 that reasonably and appropriately protect the confidentiality, integrity, and availability of any Protected Health Information that it creates, receives, maintains, or transmits.

Regarding use of QuitGuide, we do not have access to automated data from app use. As such, use and engagement data will be self-reported on electronic CRFs via online questionnaires completed by study participants. The QuitGuide app is maintained by the U.S. Government. It is protected by various provisions of Title 18, U.S. Code. The QuitGuide app notes, "NCI complies with requirements for privacy and security established by the Office of Management and Budget (OMB), Department of Health and Human Services (DHHS), and the National Institutes of Health (NIH)."

